Final Dietary Counselling Session	-discussion about achievements made during the program and affirmations -discussion of long-term goals and strategies to maintain
-----------------------------------	--

Dietary Supplement

During the 12-week study period, participants will be supplied with an omega-3 capsule supplement (AquaOmega High EPA) and instructed to take a dose of four capsules, once daily (containing a total of 3456 mg of omega-3 fatty acids: 2659mg of Eicosapentaenoic acid (EPA), 532mg of docosahexaenoic acid (DHA), and 800IU of Vitamin D), with a meal. Significantly more trials have been completed using omega-3 supplementation in the treatment of depressive disorders than anxiety disorders(42). Recent guidelines recommend a daily dose of 1-2g of EPA with a ratio of EPA:DHA of at least 2:1 for the treatment of depression(43). Due to the lack of specific recommendations on dose of omega-3 use for anxiety, our intervention will draw inference from these guidelines on depression to employ a dose that has been shown to be beneficial in other psychiatric disorders. We have selected a high dose, high EPA formula in order to maximize the likelihood of detecting a signal of effect in the present pilot trial.

Concomitant Therapies

All concomitant medication, psychotherapy or natural health products will be allowed during this trial. In order to minimize the risk of adverse events related to hypervitaminosis D, participants who are supplementing 1701 to 4000IU of vitamin D daily at the time of screening will be eligible to participate if they agree to decrease their vitamin D supplementation to 1700 so that their total daily intake of vitamin D, including the study product, is 2500IU. Participants will be encouraged to continue all other previous treatments at the same dose for the duration of the trial, if possible, but allowed to make changes if recommended by their mental health care provider. Participants will be queried at baseline

and at each follow up visit about their use of medication, psychotherapy or natural health products and any changes will be recorded, analyzed, and reported.

Safety and Criteria for Withdrawal

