As rescue medicine, participants will be advised to take the over-the-counter product, diphenhydramine (Benadryl), in the event of an allergic reaction to the study product or any of the new foods that they consume, as recommended on the product label. Diphenhydramine will be provided to participants with the study product. Participants will be queried about use of the rescue medication and asked to return any unused product at the end of the trial. The use of rescue medication for an allergic reaction will be recorded. Participants will be instructed to contact the study coordinator immediately if they experience a negative reaction to the study product or a serious worsening of their health. They will be provided with an email and phone number for this purpose. The qualified investigator will assess the patient and recommend a course of action. If the participant requires medical visits or medications that are not reimbursed by the Ontario Health Insurance Plan (OHIP), these costs will be reimbursed by the study sponsor, the Canadian College of Naturopathic Medicine. At each study visit, participants will be asked if they have experienced any negative effects since beginning the study product. Participants will be withdrawn from the study if they experience an allergic response, or other serious adverse event, as a result of the study product. These participants will be referred to their primary health care provider or a walk-in clinic for management. Participants will also be withdrawn if the trial psychiatrist deems the participant not adequately stable to continue to participate in the trial. This includes the presence of severe suicidal ideation or symptoms of psychosis. At each follow up visit, participants will be asked by the intervention deliverer if they have experienced a significant worsening in their mental health since the previous visit. If they report symptoms related to suicidal ideation, the Ask Suicide-Screening Questionnaire (ASQ) will be completed(44). If the participant screens positive, they will be referred to

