the study psychiatrist for a complete assessment. If they screen acute positive, they will be referred directly to a crisis center or the hospital emergency room. If they report any symptoms related to psychosis (any report of hallucinations, delusions, or disordered thinking), the participant will be referred to the study psychiatrist for assessment. If they meet criteria for withdrawal, they will be referred to their current mental healthcare provider for appropriate assessment and treatment. If a participant reports a significant worsening in symptoms of anxiety or depression, they will be permitted to remain enrolled in the study. They will be encouraged to contact their primary mental health care provider for assessment and management. If the mental health care provider suggests that psychiatric rescue medication is needed, this clinician will recommend the treatment to the participant. If rescue medication is used for mental health symptoms, participants will be allowed to continue participating in the study. The use of rescue medication will be queried at each study visit and recorded. Given that the primary objective is feasibility and acceptability, participants with poor compliance with the study intervention will not be withdrawn from the study.

Expected adverse events for this study product include fishy aftertaste, bad breath, heartburn, nausea, or loose stools, atrial fibrillation, increased bleeding. All adverse events will be recorded, and these records will be maintained for 15 years. The clinical trial sponsor will inform the Natural and Non-prescription Health Product Directorate of Health Canada of any serious expected or unexpected adverse events related to the study product immediately if possible and no later than seven days after becoming aware of the information. Serious adverse events will also be reported to the Research Ethics Board that has reviewed the study protocol.

Participants will be withdrawn from the study if their baseline serum levels of 25-hydroxy-vitamin-D is greater than 120 nmol/L, as this level has been associated with safety concerns(45). These individuals will be instructed to contact their primary health care provider for assessment and management. In the event that the baseline or final blood work assessment suggests the presence of an undiagnosed

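### Atrial fibrillation and increased bleeding are listed as expected adverse events, but no scheduled item asks about either, so capture depends on participants volunteering symptoms

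*Combined protocol and SAP*

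**What the plan says.** Under Safety and Criteria for Withdrawal, the protocol puts minor and potentially serious effects in one list: "Expected adverse events for this study product include fishy aftertaste, bad breath, heartburn, nausea, or loose stools, atrial fibrillation, increased bleeding".

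The same section describes how events come to light:

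- Scheduled: "At each study visit, participants will be asked if they have experienced any negative effects since beginning the study product". Supplemental File 2 has a matching adverse-events row marked across the session columns.
- Unscheduled: "Participants will be instructed to contact the study coordinator immediately if they experience a negative reaction to the study product or a serious worsening of" health in general. The step after that call: "The qualified investigator will assess the patient and recommend a course of action".
- Recording: all adverse events are to be recorded, with no threshold for seriousness or attribution.

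A separate mental health enquiry runs alongside at every follow-up: "participants will be asked by the intervention deliverer if they have experienced a significant worsening in their mental health since the previous visit". Those who report significantly worse anxiety or depression may stay enrolled, and "They will be encouraged to contact their primary mental health care provider for assessment and management".

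One of several withdrawal rules concerns product-related events: "Participants will be withdrawn from the study if they experience an allergic response, or other serious adverse event, as a result of the study product". Others cover the trial psychiatrist's judgement of stability and a high baseline vitamin D level.

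**The concern.** The plan names two potentially serious effects and then describes no step aimed at finding them. An open question finds what the participant notices, considers relevant and chooses to mention. Bruising may simply go unsaid. A rapid or irregular heartbeat has a further problem: everyone enrolled has moderate to severe anxiety, and a separate question invites reports of worse mental health. A participant could reasonably describe the heartbeat in answer to that question instead. The text that follows from such a report sends her towards her mental health provider and does not mention adverse-event recording or a possible physical or product-related cause.

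The pilot is meant to lay the groundwork for a larger trial. If it reports no rhythm or bleeding events, readers of that trial's protocol need to know whether anyone asked.

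**Working it through.** The documents give no event rate for either risk and no sample size calculation, so there is no stated figure to reproduce. The check has two parts.

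**Part 1: how each named risk is handled**

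| Risk | Eligibility | Baseline or scheduled item | Specific rule |
|---|---|---|---|
| Vitamin D excess | Exclusion above 4000 IU daily | Baseline serum level | Withdrawal above 120 nmol/L; intake condition |
| Allergy | Exclusions for fish, ingredients and severe food allergy | Rescue product use queried | Withdrawal rule |
| Suicidality | Exclusion if high | Screening scale; follow-up question | Named triggers and referral |
| Atrial fibrillation | None | Open question only | None specific |
| Increased bleeding | None | Open question only | None specific |

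Two items might be mistaken for coverage.

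- Outcomes Measured lists hemoglobin, but among the blood sugar markers. Supplemental File 2 gives it as hemoglobin A1C, so it is not a check for blood loss.
- Concomitant Therapies provides for medication use to be queried at baseline and each follow-up. That could reveal a relevant drug, but it does not ask about rhythm or bleeding history.

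The schedule contains no pulse, ECG or coagulation test. Four of the seven sessions are by video, so most contacts rely on what is asked and answered.

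**Part 2: what a count of zero would mean**

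Inputs: 50 participants planned, 25 starting at once and 25 after the waitlist, all due to receive the product (Trial Design and Setting).

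One-sided 95% upper bound for zero events in n, with every event captured: 1 − 0.05^(1/n).

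- n = 50: 1 − 0.05^(1/50) = 5.8%
- n = 25: 1 − 0.05^(1/25) = 11.3%

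Chance of recording at least one event in 50: 1 − (1 − p·s)^50, where p is the true risk over the intervention and s the share of events captured. Both are assumptions, so a range is shown.

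| True risk p | s = 100% | s = 75% | s = 50% | s = 25% |
|---|---|---|---|---|
| 0.5% | 22.2% | 17.1% | 11.8% | 6.1% |
| 1% | 39.5% | 31.4% | 22.2% | 11.8% |
| 2% | 63.6% | 53.0% | 39.5% | 22.2% |
| 5% | 92.3% | 85.2% | 71.8% | 46.7% |

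At a true risk of 2%, for example, the chance of seeing any event falls from 63.6% to 39.5% if half of events go unreported. The number of participants sets the first column. Ascertainment decides how far to the right the trial sits.

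**The case against.** The strongest reply is that the plan already has adequate routes. The open question asks about effects since the product was started. That is a time window, and it does not require the participant to blame the capsules. The call-in instruction covers serious worsening of health from any cause and leads to the qualified investigator. All adverse events are recorded. The satisfaction survey in Supplemental File 4 also asks what participants disliked about the supplement. All of this stands, and it rules out saying that the plan has no means of detecting these events. But each route waits for the participant to raise the symptom.

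Several stronger readings are tempting and are not supported:

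- A reader might infer that the protocol sends palpitations to the mental health provider. It never mentions palpitations. That route applies only to symptoms presented as worse anxiety or depression, does not replace the open question, and may lead to a family doctor. Mislabelling is a plausible failure that the text does not guard against, and it cannot apply to bleeding.
- A reader might infer that only an allergic or serious product-related event leads to withdrawal. Other grounds are stated.
- A reader might set the 2659 mg of EPA against the range in "Recent guidelines recommend a daily dose of 1-2g of EPA with a ratio of EPA:DHA of at least 2:1 for the treatment of depression(43" and read 2659/2000 = 1.33 as a measure of added risk. That range concerns treatment of depression and is not a safety limit, so the ratio says nothing about rhythm or bleeding.

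It is also fair to say that no questioning method would make zero in 50 reassuring, and that the analysis is descriptive. That limits what is at stake but does not favour the weaker method.

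**Conclusion.** The concern holds as one of ascertainment. Two effects that the plan itself expects have no directed question, baseline item or eligibility criterion, while vitamin D excess, allergy and suicidality each receive specific handling. The worsening-anxiety text also has no stated connection to adverse-event recording.

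The size is modest and cannot be pinned down from the documents. With full capture, zero in 50 is compatible with a risk of up to about 5.8%, and any shortfall in capture weakens that further. The capture shares in the table are assumptions with no source in the documents. Treating these two effects as the most serious on the list is a judgement, since the protocol does not rank them.

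One limit applies: the electronic case report form is not shown and the consent pages were not available, so prompts or warnings may exist there. The change is recommended, but the pilot's feasibility objective does not depend on it.

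**What to change.** Add two directed items to the adverse-event question at each session: rapid or irregular heartbeat, and unusual bleeding or bruising. Record any positive answer as an adverse event, whatever the participant attributes it to. At baseline, record any history of rhythm or bleeding problems alongside the medication query already planned. If the case report form already contains such prompts, a sentence in the safety section saying so would meet the point on elicitation.

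The sponsor should also reconcile the expected-event list with the eligibility, worsening-anxiety and withdrawal text, and state how a symptom reported as anxiety enters adverse-event recording. How such participants are managed clinically is for the sponsor and investigator to decide.

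The cost is at most 2 × 7 = 14 short questions per participant, or 14 × 50 = 700 across the trial, plus one baseline item. No new procedure is needed. The downside is more non-specific heartbeat reports in an anxious sample, which someone has to review.

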will be measured before and after the waitlist period and the intervention period. Body mass index and change in weight during the intervention and control period will be calculated. These data will characterize the study participants and allow for assessment of confounding factors.

In order to assess changes in anxiety symptom severity, the Beck Anxiety Inventory, a validated, 21-item self-report inventory for measuring the severity of anxiety in participants with psychiatric illness, will be administered(49). The impact on quality of life will be assessed using PROMIS-29(50). In order to assess the impact of the intervention on behaviour change and qualitatively assess the acceptability of the intervention, questionnaires related to mindful eating and diet quality will be administered before and after the intervention. Mindful eating behaviours will be measured using Mindful Eating Questionnaire (MEQ) which has been validated for use in a diverse adult population(51). Changes in diet quality will be measured using the MEDI-LITE score, a concise tool for measuring consistency with the Mediterranean diet, which has been validated for use in adult populations(52). Changes in self-efficacy will be assessed using the General Self-Efficacy Scale(53). Changes in diet quality will also be assessed objectively through blood tests. Omega-3 fatty acids levels will be assessed using the dried blood spot test, Omega Score(54), which represents summed EPA, DHA and Docosapentaenoic acid as a percentage of the total fatty acids in whole blood. Analysis will be completed by Lipid Analytical Laboratories. Additional assessment will be completed to measure fasting serum cholesterol panel, markers of blood sugar levels and regulation (Hemoglobin, fasting insulin, fasting glucose and calculated HOMA-IR(55, 56)), vitamin C, beta-carotene, and C-Reactive Protein. These analyses will be completed by LifeLabs. Completion of the questionnaires and blood tests will be done at baseline, at the end of the waitlist control period (for participants assigned to this group) and at the end of the intervention. Participants who do not attend all of the scheduled visit but have not withdrawn will be contacted to complete the questionnaires and blood tests. See Supplemental File 4 for a summary of assessments on participant demographics, satisfaction with the dietary intervention, the research program, and participant experience.

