Compliance with the supplement will be assessed at the final visit. Participants will be instructed to bring back all study product bottles containing any remaining capsules. The remaining capsules will be counted and recorded by a member of the study team. Compliance with the supplement will be reported as a percentage based on calculating the amount of pills consumed in comparison to the amount expected according to instructions.

Statistical Analysis

Since the pilot study is not powered to demonstrate efficacy, analysis of the pilot study results will be strictly descriptive. Baseline demographics and outcome measures will be summarized by group as means and confidence intervals, medians and interquartile ranges, or percentages and confidence intervals as appropriate. Process evaluation will be described both quantitatively (percent screened positive for inclusion, percent of eligible patients who consent to participate, percent with significant protocol violations, etc.) and qualitatively (e.g., reasons for failing inclusion criteria, reasons for refusing to participate, participant impressions of the intervention, etc.). All participants will be analyzed in the group to which they were randomized. Missing data will be carefully documented to inform the design of the larger trial. Participants who complete the treatment but do not report a satisfaction level will be treated as 'unsatisfied.' No interim analysis will be undertaken. The study will be considered feasible if 50 participants are recruited within two years, and participants in the intervention group take at least 60% of the study product and attend at least 60% of the diet counselling sessions. The study will be considered acceptable if at least 70% of participants report that they were satisfied with the intervention. The statistical analysis plan for the full-scale trial is included in Supplemental file 5.

Data management

The collection and storage of data will be done according to Good Clinical Practice Guidelines. All study staff involved in the collection or entry of data will be trained by the trial coordinator and will complete

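### The Omega Score cannot serve as an objective measure of diet quality, because the capsules supply the same fatty acids and their effect cannot be separated from a change in diet

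*Combined protocol and SAP*

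**What the plan says.** Outcomes Measured first names MEDI-LITE, a questionnaire score, for change in diet quality. It then adds a second route: "Changes in diet quality will also be assessed objectively through blood tests". The next sentence begins "Omega-3 fatty acids levels will be assessed using the dried blood spot test" and identifies the test as the Omega Score, "which represents summed EPA, DHA and Docosapentaenoic acid as a percentage of the total fatty acids in whole blood". A further panel follows, including vitamin C and beta-carotene. Blood is taken at baseline, at the end of the wait (waitlist arm) and at the end of the intervention.

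Under Dietary Supplement, participants are "instructed to take a dose of four capsules, once daily", "containing a total of 3456 mg of omega-3 fatty acids", of which 2659 mg is EPA and 532 mg is DHA. Trial Design and Setting describes the control as a waitlist without treatment. There is no counselling-only or capsule-only arm.

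Uptake of the capsules is measured separately: "Compliance with the supplement will be reported as a percentage based on calculating the amount of pills consumed". Statistical Analysis sets the feasibility threshold at 60% of the product.

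**The concern.** Two of the three fatty acids in the score are delivered directly by the study product. A woman who takes her capsules and eats exactly as before would be expected to show a higher score after 12 weeks, while a woman still waiting gets no study capsules. Read as the protocol has it, that difference would be reported as objective evidence of better diet quality.

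Change in diet quality is a stated secondary objective. The blood tests are there to give it support that does not depend on self-report. A marker that moves without any dietary change could appear to corroborate a questionnaire result that it does not bear on, and that reading could carry into the planning of the full-scale trial.

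**Working it through.** **Inputs from the documents**

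- EPA 2659 mg/day, DHA 532 mg/day, total omega-3 3456 mg/day (Dietary Supplement).
- Intervention period of 12 weeks, or 84 days.
- Entry is refused when the baseline Omega Score is above 5% (Participants Eligibility), so women start with low values.
- Fish twice a week appears once, as an example of a goal (Supplemental File 3). The documents give no EPA or DHA content for fish.

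**Capsule dose**

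- EPA + DHA: 2659 + 532 = 3191 mg/day, about 3.2 g.
- Remaining omega-3, not itemised: 3456 − 3191 = 265 mg/day.
- Over the intervention at full compliance: 3191 × 84 = 268,044 mg, about 268 g.
- At the 60% threshold: 0.60 × 3191 ≈ 1915 mg/day.

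**Can the two sources be separated?**

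| Comparison | Counselling differs? | Capsules differ? |
|---|---|---|
| Immediate arm v waitlist arm at 12 weeks | yes | yes |
| Waitlist arm, end of wait v end of intervention | yes | yes |

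In both available contrasts the two components change together, so a change in the score cannot be assigned to one of them. This needs no assumption about fish, and no section describes a method for separating them.

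**Which source is likely to dominate?**

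This part rests on an assumption. Suppose the fish goal is met in full by women who ate no fish before, and let one serving contain *s* mg of EPA plus DHA. The diet then adds 2*s*/7 mg/day, and the capsule share of added intake is capsule ÷ (capsule + 2*s*/7).

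| Assumed *s* (mg) | Diet adds (mg/day) | Share at full compliance | Share at 60% |
|---|---|---|---|
| 300 | 86 | 3191/3277 = 97% | 1915/2001 = 96% |
| 1000 | 286 | 3191/3477 = 92% | 1915/2201 = 87% |
| 2000 | 571 | 3191/3762 = 85% | 1915/2486 = 77% |
| 3000 | 857 | 3191/4048 = 79% | 1915/2772 = 69% |

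For diet merely to equal the capsules, each of the two servings would have to supply 3191 × 7/2 ≈ 11,170 mg at full compliance, or 1915 × 7/2 ≈ 6,700 mg at 60%.

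These are shares of intake. They are not shares of the change in a whole-blood percentage that also counts DPA, and they only show why capsules are likely to be the main source.

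**The case against.** The strongest reply is that the problem is one loosely placed sentence. The Omega Score's own sentence says that it measures omega-3 levels. Objectives lists biomarkers separately from diet quality, so the score has another natural home. MEDI-LITE is already the named diet-quality measure, and the blood tests are an addition to it. All of this is true and it limits the reach of the point. It does not remove it: the sentence that introduces the blood tests gives their purpose as diet quality, and the score is the first test named under it.

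Several stronger readings are tempting, and the documents do not support them:

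- *The score is the main objective endpoint for diet.* No ranking is given. It is only mentioned first.
- *The trial could declare success on it.* Statistical Analysis is descriptive. Its criteria use recruitment, product taken, attendance and satisfaction, and Supplemental File 5 makes the Beck Anxiety Inventory the primary outcome of the full-scale trial.
- *A rise would say nothing about diet.* Eating more fish may add something. The exact statement is that the rise is mainly from capsules and cannot be separated.
- *The whole blood panel fails.* Vitamin C and beta-carotene are not among the product's stated contents. They have a milder weakness of their own: Concomitant Therapies allows other natural health products, which could move them, although changes in use are recorded.
- *The capsule count is an error in the plan.* A count cannot tell swallowed from discarded capsules, but that limitation is common to all such counts. The score is collected in any case, so a comparison remains possible.

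**Conclusion.** The point holds. The Omega Score cannot support a conclusion on change in diet quality here, because the intervention supplies 3191 mg/day of EPA plus DHA and every available contrast changes capsules and counselling together. That the sources cannot be separated follows from the design alone. That capsules are the main source rests on the dose set against an assumed fish content; over the range of 300 to 3000 mg per serving the direction does not change.

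The consequence is modest: misattribution in one of several measures of a secondary objective in a descriptive pilot. The feasibility and acceptability criteria are untouched. The correction is still worth making, since it changes what may be concluded from data that will be collected anyway.

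**What to change.** In Outcomes Measured:

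1. Reclassify the Omega Score as a marker of omega-3 status and supplement exposure, and state that no conclusion on diet quality will be drawn from it.
2. Keep MEDI-LITE as the diet-quality measure and name vitamin C and beta-carotene as its supporting objective markers. Say that these will be read alongside the recorded use of other natural health products.
3. Optionally, report the change in the Omega Score descriptively beside the capsule count as a cross-check on uptake. The 60% criterion stays as it is, based on the count.

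The cost is a few sentences and the usual notice of an amendment to the ethics board, the regulator and the registry. No test, sample or visit is added, and nothing in the intervention changes.

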For participants randomized to the waitlist control group, the baseline visit will conclude with instructions for the waitlist period. Participants randomized to the immediate start group will immediately begin the first dietary counselling session. There is no predetermined time between baseline data collection and commencement of the intervention; once all baseline electronic data are collected, participants may schedule the first in-person visit which will include the collection of the remaining baseline data and the first intervention session.

The Intervention

The intervention will consist of seven dietary counselling sessions delivered over 12 weeks (one session every two weeks). Three visits (the first, fourth, and seventh) will take place in person and the remaining will take place by secure video platform. If participants do not have access to a computer or the internet, they may complete all sessions in person. In the event that COVID-19 restrictions change during study delivery, the number of virtual sessions may be altered in order to comply with local restrictions. The sessions will be 45 to 60 minutes in length.

Intervention Development

The dietary recommendations are based on the Mediterranean diet(35) with minor modifications based on the results of a recent scoping review which identified and collated all of the existing research on diet

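### The available text does not provide for 12-week outcomes from formally withdrawn participants, and in the randomised 12 weeks the withdrawal triggers act mainly in the immediate-start arm; the effect on the descriptive BAI comparison is probably small and of uncertain direction

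*Combined protocol and SAP*

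**What the plan says.** Outcomes Measured places questionnaires and blood tests at baseline, at the end of the wait (waitlist arm) and at the end of the intervention. For missed visits it says: "Participants who do not attend all of the scheduled visit but have not withdrawn will be contacted to complete the questionnaires and blood tests".

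Safety and Criteria for Withdrawal gives two rules that can operate after randomisation. One is product-related: "Participants will be withdrawn from the study if they experience an allergic response, or other serious adverse event, as a result of the study product". The other is psychiatric: "Participants will also be withdrawn if the trial psychiatrist deems the participant not adequately stable to continue to participate in the trial"; severe suicidal ideation and psychotic symptoms are the examples given. A third rule, 25-hydroxy-vitamin D above 120 nmol/L, uses the baseline value.

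Instability is looked for as follows: "At each follow up visit, participants will be asked by the intervention deliverer if they have experienced a significant worsening in their mental health". Participants are also told to "contact the study coordinator immediately if they experience a negative reaction to the study product or a serious worsening of their health".

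The waitlist arm has no counselling visits during the wait. Pre-study Screening, Randomization and Baseline Evaluation says: "For participants randomized to the waitlist control group, the baseline visit will conclude with instructions for the waitlist period". The schedule in Supplemental File 2 shows that arm's next contact at Day 85.

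The same safety section also keeps people in. On symptoms: "If a participant reports a significant worsening in symptoms of anxiety or depression, they will be permitted to remain enrolled in the study". Users of psychiatric rescue medication also stay, and "participants with poor compliance with the study intervention will not be withdrawn from the study".

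Statistical Analysis is descriptive and as randomised, and missing data are to be documented.

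**The concern.** Analysing people in the arm to which they were randomised helps only if they have an outcome. Someone who stops the product after an allergic reaction could still answer an online questionnaire at week 12, but the text ties stopping for safety to leaving the study, and leaving the study to not being contacted.

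During the wait a waitlisted participant takes no product, so the product rule cannot apply to her. The psychiatric rule names no arm, but routine questioning takes place only at intervention visits, so instability is more likely to be noticed in the immediate-start arm. That second asymmetry is one of detection only.

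What is at stake is the descriptive comparison of anxiety change against the waitlist period, a secondary objective. No feasibility or acceptability criterion uses the BAI. The point has more weight if the rule is carried into the full-scale trial, where Supplemental File 5 makes 12-week BAI the primary outcome, analysed by ANCOVA, and names no handling of missing outcomes.

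**Working it through.** The documents give no BAI standard deviation, withdrawal rate or sample-size calculation, so there is no planned figure to reproduce. Only the 25 per arm comes from the protocol (Trial Design and Setting); the other inputs are assumptions.

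**Which rules differ by arm in the randomised 12 weeks**

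| Rule | Immediate start | Waitlist |
|---|---|---|
| Product-related allergy or serious adverse event | Can occur | Cannot occur |
| Psychiatric instability | Asked about at each follow-up visit | Self-report only |
| Baseline vitamin D | Same rule | Same rule |
| Worsening anxiety or depression, rescue medication, poor compliance | Stays in | Stays in, where applicable |

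**Precision of the comparison**

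95% half-width = t(0.975, 48 df) × SD × √(2/25). With SD 10 this is 2.011 × 10 × 0.2828 = 5.69. With SD 8 it is 4.55, and with SD 12 it is 6.82. With 23 against 25 observed and SD 10 it is 5.8.

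**Shift from lost outcomes**

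Let k of 25 be lost and let D be the mean BAI of those lost minus the mean of those retained. The full-arm mean is the retained mean plus (k/25) × D, so the retained mean is off by (k/25) × D. A positive D makes the immediate-start arm look better.

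| k lost, immediate start only | D | Shift | Share of 5.69 |
|---|---|---|---|
| 1 | +10 | 0.4 | 7% |
| 2 | +10 | 0.8 | 14% |
| 3 | +15 | 1.8 | 32% |
| 2 | −5 | −0.4 (against the intervention) | 7% |

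If both arms lose 2 people with D = +10, the shifts cancel. If both lose 2, with D = 0 in the immediate-start arm and +10 in the waitlist arm, the comparison moves 0.8 points against the intervention.

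**What D = 10 means as a correlation**

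At q = 2/25 = 0.08, the ordinary correlation between being withdrawn and week-12 BAI is D × √(q(1−q))/SD = 10 × √(0.08 × 0.92)/10 = 0.27. On a latent-liability scale it is about 0.5: 0.5 × 10 × φ(z)/(1−q) = 0.81, with z the normal quantile at 0.08. The scales must not be mixed, since an ordinary correlation of 0.5 would give 0.5 × 10 × √(0.08/0.92) = 1.47 points.

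**If the rule is carried into the full-scale ANCOVA**

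Assume a baseline to week-12 correlation of 0.5, and that those lost were 5 points higher at baseline (0.5 × 10). The adjusted shift is 0.08 × 10 − 0.5 × (0.08 × 5) = 0.8 − 0.2 = 0.6, whatever the sample size. The half-width is t × 10 × √(1 − 0.25) × √(2/n): 4.93 at 25 per arm and 2.42 at 100. The shift rises from 0.6/4.93 = 12% to 0.6/2.42 = 25% of the half-width.

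**The case against.** The strongest reply is that the gap is inferred. The sentence under Outcomes Measured limits who is chased after missed visits; it does not forbid a final assessment at withdrawal. Consent pages are not in the available text and could deal with data after withdrawal. A reader might infer that the plan rules out such outcomes. The documents do not support that; they support only that the available text makes no provision for them.

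The second reply is that little is left to lose. Those most likely to distort the BAI are kept: people whose anxiety or depression worsens, rescue-medication users and poor compliers. Entry criteria exclude current high suicidality, psychotic disorder and allergy to fish or product ingredients, so withdrawals under these rules should be few. This stands, and it keeps the point small.

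A reader might also infer that the rule flatters the intervention. Psychiatric withdrawals alone would tend to remove high scores from the immediate-start arm, but allergy or adverse-event withdrawals imply no clear BAI direction, and waitlisted participants can self-report or leave by choice. The documents fix no sign.

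Nor would the pilot teach much about how many withdrawn people respond. If 1 of 2 answered, the exact 95% interval would be 1% to 99%; if both did, 16% to 100%.

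Finally, Supplemental File 5 is a short analysis outline without withdrawal rules, so the full-scale calculation is conditional, and any fixed bias grows relative to a narrowing interval. That is fair, but it is still a reason not to carry the rule forward.

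**Conclusion.** The point holds in a limited form, as an optional improvement. The text removes people from the study for safety reasons, re-contacts only those not withdrawn, and applies triggers that fall mainly, though not only, on one arm in the randomised period. The pilot's feasibility and acceptability conclusions are unaffected.

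For the secondary BAI description, one or two losses with D of 10 give a shift of 0.4 to 0.8 points, or 7% to 14% of the half-width. Three losses with D of 15 would give about a third. These figures rest on assumed numbers lost, score differences and SD, and on no comparable loss from the waitlist arm. Comparable losses there would shrink, cancel or reverse the shift. A claim of material bias, or of bias in a known direction, would go beyond the documents.

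**What to change.** In Safety and Criteria for Withdrawal, separate stopping the product or counselling from leaving the study. When treatment stops remains a clinical decision.

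Under Outcomes Measured, add a sentence to this effect: randomised participants withdrawn for safety or clinical reasons will still be sent the online questionnaires due at the end of their current 12-week period, unless they withdraw consent to data collection or a clinician judges contact unsuitable, in which case that reason is recorded. Limit this to questionnaires. Merely deleting the not-withdrawn condition from the existing sentence would also call withdrawn people back for fasting blood tests.

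When documenting missing data, show withdrawals and missing outcomes by arm and reason. Carry the same rule into the full-scale trial.

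The cost is minor protocol and consent wording and a few extra questionnaire requests through the existing REDCap system, with no added visit. Recovery will be incomplete among acutely unwell people, so part of any shift could remain.
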